8. Describe the power analysis used and cite your method of statistical analysis. If a power analysis is not possible, thoroughly justify the sample size required for the study, including appropriate literature citation (alternatively provide page reference in attached protocol):

The data will be presented as mean \pm SD, analyzed using the conditions x time analysis of variance (ANOVA), while BHI will be analyzed using a one-way ANOVA. Tukey post-hoc testing and contrast analysis can be used as appropriate. Statistical significance was set at p \leq 0.05.

We aim to have 30 subjects complete the study. This is a pilot study to inform a future large-scale trial with appropriate power calculation.

Research Activities

 * Provide a detailed description of all research activities (including screening and follow-up procedures) that will be performed for the purpose of this research study. This description of activities should be complete and of sufficient detail to permit an assessment of associated risks.

Prior to initiation of the study, subjects will complete a brief phone screen to assess basic eligibility and will be asked to fast. The screening visit will consist of informed consent, health history, and discussing eligibility requirements for each study visit, including (1) refrain from vigorous exercise for 24 hrs prior, (2) fast overnight for at least 10 hrs, (3) empty bowel and bladder upon waking up, (4) can consume one 8oz cup of coffee or tea. For female subjects, this will also include their last date for menstruation and/or birth control method to take into consideration the effects of ovulation on water retention.

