Prior to all research visits (screening, visits 1, 2, and 3), participants must refrain from vigorous exercise (exercises that results in a high heart rate and rapid breathing) within 24 hours of study visit. Participants will fast (food) overnight for 10h prior to initiation of test. Upon waking they are asked to empty their bowel and bladder. They can consume one 8oz cup of coffee or tea (plain with no sugar or additives) to reduce caffeine headaches. They will present at 7-8am, which will be pre-specified. Prior to emptying their bladder, a blood draw of up to 1 ml will be drawn by a trained phlebotomist for the i-STAT testing, which will be used to measure creatine and electrolytes. After this they will be asked to empty their bladder. Immediately after emptying the bladder, bioimpedence will be measured. Females will be administered a urine pregnancy test. A urinalysis dipstick for protein/blood/glucose and i-STAT measurement for creatinine and electrolytes will be completed to confirm eligibility. Next, the subject will be asked to rest for 5 mins, after which baseline vitals will be taken, including blood pressure, heart rate, weight. For Visit 2 and Visit 3, the participant will be asked to review medical history and any change in status may warrant an additional baseline creatinine and blood/protein test to confirm eligibility. All studies will be repeated in the same subject using either Buoy (intervention) or water (control) or Nuun (intervention). Urine will be collected at four specific timepoints during the intervention and the volume will be recorded. If participants need to urinate between scheduled collection times, urine will be collected, volume recorded, and combined with the urine collection of the following timepoint. These urine samples will be measured and a fraction of it will be sent to the lab to be tested for the following electrolytes: sodium, potassium, chloride and urine osmolarity. Urine creatinine will also be tested at these timepoints. Additional food or beverage will not be allowed throughout the study period.

VISIT 1---BUOY INTERVENTION: The goal is to give 600mg of Na+ over 4 hours while measuring urine output over 6 hours. The recommended Buoy dosage is ¹/₃ tsp in 237 ml of water (50mg Na+) multiple times a day (Table 1). Therefore, to safely achieve a total dose 600mg Na+ (6-fold increase from single dose) we will use 4 tsps (18 ml) of Buoy diluted in 1 L of water.

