Prior to initiation of test blood pressure and heart rate will be measured. Urine will be collected and discarded.

At time 0, the participant will begin to drink fluid (drinking 6.25% of their total amount every 15 min). Urine will be collected at 60, 120, 240, and 360 min. Bioimpedence will be measured after each urine collection. Collect urine for a total of 6 hours. VISIT 2—WATER CONTROL: Participants will ingest 1 L of water at a rate of 6.25% of the calculated amount of water every 15 min for 4 hours.

Prior to initiation of test blood pressure and heart rate will be measured. Urine will be collected and discarded.

At time 0, the participant will begin to drink fluid (drinking 6.25% of their total calculated amount every 15 min). Urine will be collected at 60, 120, 240, and 360 min. Bioimpedence will be measured after each urine collection. Collect urine for a total of 6 hours.

VISIT 3—NUUN INTERVENTION: The goal is to give a one-time dose of 2 tablets of Nuun Sport (600mg Na+) at the start of the trial, diluted in 1L water to be consumed within 30 min (similar to prior published data, Pence 2020).

Prior to initiation of test blood pressure and heart rate will be measured. Urine will be collected and discarded.

At time 0, the participant will consume the beverage over 30 min. Urine will be collected at 60, 120, 240, and 360. Bioimpedence will be measured after each urine collection. Collect urine for a total of 6 hours. Patients will be compensated \$300 after completion of three visits.

Buoy is an all-natural, organic, FDA compliant dietary electrolyte supplement that can be dissolved in 8-12oz water (or other liquid) and provide electrolytes in servings of 1/3 teaspoon. Nuun are electrolyte tablets that are added to water to improve fluid balance and beverage hydration index (BHI) in healthy individuals (Pence, 2020). Nuun tablets contain a mix of electrolytes, including calcium, magnesium (as an oxide), chloride, sodium, and potassium. The recommended use of Nuun is one tablet dissolved in water, administered once daily.

The PI and study team will be performing the research procedures. A phlebotomist will be used to complete the blood draws.

Following each study visit, a boxed lunch will be offered to each participant. This lunch will be Jimmy John's (or a similar sandwich shop). Each participant will be asked about preferences and food allergies during the screening process so provide an appropriate option for participants involved.

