 Upload a copy of all materials used to collect data about subjects: (Attach all surveys, interview/focus group scripts, and data collection forms except for case report forms, SCID or KSADS):

 Document
 Category
 Date Modified
 Document History

 view
 Buoy Patient Data Sheet(1)
 Data Collection
 7/6/2023
 History

3. * Will blood samples be obtained for research purposes?

• Yes O No

* Provide the volume per withdrawal, total volume and frequency, and qualifications of individual performing the procedure:

Venous whole blood will be collected using phlebotomy and up to 1 ml will be collected to be analyzed using an i-STAT. Blood will be collected for i-STAT analysis during the screening visit. For Visit 2 and Visit 3, the participant will be asked to review medical history and any change in status may warrant an additional baseline blood test to confirm eligibility.

Blood will be drawn by a trained phlebotomist.

Consent Process

Enter N/A in response to the following questions if a Waiver of Consent is requested for all research activities or if no subjects are being enrolled.

1. * Indicate where the consent process will take place and at what point consent will be obtained:

The consent process will take place prior to the initiation of study procedures. eConsent will be collected prior to the screening visit and Visit 1 in order to minimize the time spent by each participant during the first visit. eConsent will be collected using Pitt RedCap. eConsent will be signed via stylus, fingertip, or mouse.

2. * Describe the steps that will be taken to minimize coercion and undue influence, including assurance that there is sufficient time for subjects to make an informed decision:

In order to minimize the possibility of coercion or undue influence, the participants will first be informed that their choice of participation in the study is completely voluntary in nature. Prospective participants will be encouraged to ask questions and to discuss the study with others during the consent process. All of the participants questions will be addressed. It will be made clear that the participant may withdraw from the study at any time.

eConsent will be completed over the phone. An electronic copy will be provided to participants at the time of eConsent.

3. For studies that involve multiple visits, describe the process to ensure ongoing consent:

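### No urine concentration is measured before the drink at any visit, and the pre-dose bioimpedance and weight have no stated role in the analysis

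*Combined protocol and SAP*

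**What the plan says.** **Endpoints.** Study Design, item 3, lists urine volume over 6 hours, electrolytes, urine osmolarity and urine creatinine.

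**Urine before the drink.** Research Activities, item 1, has the same instruction under Visits 1, 2 and 3, just before time 0: "Urine will be collected and discarded". No volume or assay is specified for that specimen.

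**Urine after the drink.** The same item says "Urine will be collected at four specific timepoints during the intervention and the volume will be recorded". The schedule for Visits 1 and 2 is "Urine will be collected at 60, 120, 240, and 360 min", and Visit 3 gives the same four times. Of each of these collections, "a fraction of it will be sent to the lab to be tested for the following electrolytes: sodium, potassium, chloride and urine osmolarity"; creatinine is tested at the same times.

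**Other pre-dose measures.** The general paragraph of item 1 begins "Prior to all research visits (screening, visits 1, 2, and 3), participants must refrain from vigorous exercise" and goes on to the arrival sequence. That includes "Immediately after emptying the bladder, bioimpedence will be measured", a dipstick for protein, blood and glucose, and a baseline weight with the vital signs. Item 1 can be read as placing the i-STAT blood test before every visit. Item 3 is narrower: "Blood will be collected for i-STAT analysis during the screening visit", with a repeat at Visits 2 and 3 only if health status has changed.

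**Standardisation.** Items 5 (Study Design) and 1 (Research Activities) require a 10-hour food fast, no alcohol or hard exercise for 24 hours, a void on waking, arrival at 7–8 am, and at most one cup of coffee or tea, the same each time. No rule on overnight water is given.

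**Analysis.** Study Design, item 8, says the data will be "analyzed using the conditions x time analysis of variance (ANOVA"), with a one-way ANOVA for the beverage hydration index. It names no baseline term, covariate or change score.

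**Order.** Buoy is Visit 1, water Visit 2 and Nuun Visit 3. No randomised order is described.

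**The concern.** Someone who arrives short of water tends to keep more of any drink, and someone who arrives well hydrated tends to pass more. Each beverage is tested once per person, so the starting state at that one visit enters the within-person differences for Aims 1 and 3 (Buoy against water, Buoy against Nuun).

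The protocol gives reasons to expect that state to vary. Visits may be spread over three to four months, overnight water is free, and item 1 of Research Activities records menstrual dates because of their bearing on water retention. Yet the analysis has no term for starting state, and urine already in hand that could describe it is not assayed. Two things are at stake: precision in a study of 30 completers, and protection against a systematic drift in starting hydration across visits, which would coincide exactly with the change of beverage.

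**Working it through.** **1. What is available at time 0**

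| Measure | Before the drink | After the drink | Role in stated analysis |
|---|---|---|---|
| Urine osmolarity, Na, K, Cl, creatinine | none | 60, 120, 240, 360 min | endpoints, no baseline |
| 6-hour urine volume | not applicable | sum of collections | endpoint, no covariate |
| Bioimpedance | yes, after the void | after each collection | none stated |
| Weight | yes | not stated | none stated |
| Dipstick (protein, blood, glucose) | for eligibility | no | none |
| Blood i-STAT | screening; at the visits, items 1 and 3 differ | no | none |

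**2. Inputs for the size**

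The documents give no effect size, SD or correlation, so there is no plan figure to reproduce. From Study Design, item 8: n = 30 completers and a significance level of 0.05 (two-sided assumed). Assumed, with ranges:
- r, the correlation of the within-person pre-dose difference between two visits with the within-person outcome difference: 0.3, 0.5, 0.7.
- s, the systematic pre-dose shift between the two visits, in SDs of the pre-dose difference: 0, 0.25, 0.5.

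One two-visit contrast is treated as a paired t-test, a simplification of the planned ANOVA. For scale, 30 pairs give 80% power at 0.53 SD of the paired difference (noncentral t; the normal approximation gives 0.51).

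**3. Precision**

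Residual SD factor = √(1 − r²); equivalent n = 30 / (1 − r²).
- r = 0.3: √0.91 = 0.954, a fall of 5%; 30/0.91 = 33.0.
- r = 0.5: √0.75 = 0.866, a fall of 13%; 30/0.75 = 40.0.
- r = 0.7: √0.51 = 0.714, a fall of 29%; 30/0.51 = 58.8.

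These ignore the degree of freedom spent on the slope.

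**4. Bias**

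With no true beverage effect, the standardised mean outcome difference is d = r × s, and the noncentrality is d√30 on 29 degrees of freedom. For example, r = 0.5 and s = 0.25 give d = 0.125. The rejection rates are:

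| r | s = 0 | s = 0.25 | s = 0.5 |
|---|---|---|---|
| 0.3 | 5.0% | 6.8% | 12.5% |
| 0.5 | 5.0% | 10.2% | 26.3% |
| 0.7 | 5.0% | 15.3% | 45.8% |

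A simulation of 20,000 runs per cell agreed with these rates (for example 10.2% at r = 0.5, s = 0.25, and 46.2% at r = 0.7, s = 0.5). With adjustment for the pre-dose difference, every cell fell between 4.6% and 5.2%.

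The first column matters: when the visits differ only at random, the error rate stays at 5% and the loss is in precision alone.

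**5. Assay count**

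Planned: 30 × 3 visits × 4 times = 360. Added: 30 × 3 = 90, and 90/360 = 25%. If all 34 enrolled complete: 34 × 3 × 4 = 408 planned, 34 × 3 = 102 added, again 25%.

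**The case against.** Several stronger readings are tempting, and the documents do not support them.

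- *Starting hydration is never measured.* Bioimpedance follows the arrival void and weight is recorded, in a paragraph that opens with all visits. Both can be compared by condition. What is missing is any pre-dose urine concentration.
- *Discarding the void is a mistake.* Emptying the bladder is how a timed collection should start, and that urine does not belong in the 6-hour volume. The gap is the aliquot not taken first.
- *The ANOVA fails without a time 0.* It can be run on the four post-drink times, and 6-hour volume has no time-0 value by construction.
- *Any visit-to-visit difference is counted as a beverage effect.* Random differences only add error. Bias needs a systematic shift, and none is shown to exist.
- *The discarded urine is the dipstick specimen.* The protocol does not say so. The fix does not depend on it, since the urine is collected in any case.

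The remaining case against is that arrival is substantially standardised, that this is a pilot with no power target and so misses no stated precision, and that at r = 0.3 the gain is only 5% of the SD. All of that stands. It limits the importance of the point but does not remove it: overnight water stays free, the standardisation is not verified by any urine measure, and the measures that are taken have no place in the stated analysis. Aim 2 concerns an increase in total body fluid, which implies a starting bioimpedance reading, but item 8 does not say so and does not carry that reading over to the urine endpoints.

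**Conclusion.** The point holds in a limited form. No urine concentration endpoint has a pre-drink value at any visit, and the pre-dose bioimpedance and weight are not used in the stated analysis. Random differences in starting hydration are left in the error term. Systematic differences would bias the beverage contrasts and could not be separated from them as planned, because beverage and visit number coincide.

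The size is conditional. On assumed correlations of 0.3 to 0.7, adjustment would lower the residual SD by 5% to 29%, making 30 completers worth about 33 to 59. If there were also a systematic shift of 0.25 to 0.5 SD, the unadjusted false-positive rate would lie between 6.8% and 45.8%. The return to about 5% assumes a linear relation and a covariate that captures the starting state fully; an imperfect proxy would correct only part.

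This is a worthwhile, inexpensive improvement and not a fault that invalidates the trial. A reader might infer that adjustment would also resolve the fixed order. It would not: it removes only what runs through measured starting hydration, and other period effects remain.

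**What to change.** 1. **Specimen.** Keep the void before time 0 and keep it out of the 6-hour volume. Before discarding it, send an aliquot for osmolarity and, ideally, sodium, potassium, chloride and creatinine as well.
2. **Existing measures.** State under each visit that bioimpedance and weight are recorded before the drink; the visit-specific text now lists only blood pressure and heart rate.
3. **Model.** In Study Design, item 8, prespecify a repeated-measures or mixed model for 6-hour urine volume with one visit-specific pre-dose covariate: osmolarity, or the bioimpedance and weight already collected. Enter it as the deviation from the participant's own mean across visits, so that the slope is a within-person one.
4. **Baseline.** Use pre-dose values as baseline for the urine concentration endpoints only, and tabulate them by condition.
5. **Consistency.** Reconcile items 1 and 3 of Research Activities on whether i-STAT is done at every visit.

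The cost is 90 extra aliquots for 30 completers, or up to 102 if all 34 complete: about 25% more urine samples to assay, and less laboratory work if only osmolarity is tested. No new procedure or staff is needed. Using only bioimpedance and weight adds no assays, but leaves the concentration endpoints without a baseline. The values would also show whether baseline adjustment is worth planning in the larger trial that this pilot is meant to inform.
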